4. STUDY DESIGN

This study is a randomized controlled trial (RCT) with a heterogenous sample of 360 African American and Latino adolescents (ages 12-17) who do not vape; equal representation of Latinos and African Americans (180 African American adolescents and 180 Latino adolescents). After completing a preliminary baseline survey, participants will be randomized in equal numbers and representation to receive one of four (4) theoretical-based graphic messages: 1) Financial Reward, 2) Health Reward, 3) Self-efficacy, and 4) Social Norms. These graphic messages were developed in a previous research phase (STUDY00005312) using participatory research methods. See Appendix for the messages. We will assess pre- and post-exposure measures on the susceptibility of future vaping-use among African American and Latino adolescents.

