8. STUDY PROCEDURES

Once parents'/guardians' permission and adolescent's assent has been obtained, participants (n=360) will complete an individual baseline assessment on sociodemographic characteristics and susceptibility to future vaping. The survey will be hosted in REDCap, a secure, web-based system that has user-level access control. Each participant will receive a unique username and password to access the survey. At the end of the baseline assessment, participants will be randomized in equal number and representation to receive one of four (4) graphic messages: 1) health reward, 2) financial reward, 3) self-efficacy, and 4) social norms. The appropriate graphic message, available in English and Spanish, will be displayed in REDCap. Participants will be instructed to view the graphic messages carefully on their devices (e.g., desktop, laptop, tablet, and/or smartphone) and for as long as they wish. We will assess immediate post-exposure measures on susceptibility to future vaping (primary outcome). Study measures on susceptibility to future vaping are comprised of valid items derived from out and others' research. We will assess three items: (1) Are you curious about using e-cigarettes (vaping)?; (2) Do you think that you will use e-cigarettes (vaping) in the next 12 months?; and (3) If one of your best friends were to offer you an e-cigarette, would you use it? Responses include 1= definitely not, 2= probably not, 3= probably yes, 4= definitely yes. Participants will receive \$25 gift card for their time at the end of the assessment.

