17. DATA ANALYSIS PLAN

We first will perform descriptive statistics to evaluate randomization success, nonresponses, and missing data. Mean and median will be presented for continuous variables, and frequencies will be presented for categorical variables. The outcome measures will be defined as (1) a binary variable of susceptibility to future vaping (0= definitely not, 1= probably not, probably yes, definitely yes) to ease interpretation of results, and (2) the overall susceptibility score aggregating three items. Bivariate analyses will be performed, followed by multivariable modeling to compare different message groups. Logistic regression model and the analysis of covariance (ANCOVA), respectively, will be performed to control for potential confounding, and inflated type I error rate will be adjusted in multiple testing. We will also assess differences within messages by theoretical construct (reward, self-efficacy, and social norms). **Power Analysis.** The goal of this pilot analysis is to provide preliminary data for future studies, including the possible effect size. Using the ANCOVA analysis for the power calculation, we expect the effect size to be 1.05 (standardized mean difference in the aggregated score) between message groups.

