18. FUTURE RESEARCH PLANS

We will report the results of this research in one or more publications in academic journal(s) to advance knowledge pertaining to effective communication with Latino and African American adolescents regarding vaping prevention. Additionally, we will disseminate our findings at national and international conferences. We have identified a request for applications

to pursue support for this line of research through the trans-NIH Tobacco Regulatory Science Program (RFA-OD-19-019). An FDA and NIH defined priority research area is to understand how to effectively communicate to the public and vulnerable populations regarding nicotine and the health effects of tobacco products.

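### Does an unsupported expected effect size of 1.05, with no confidence interval mentioned, undermine a pilot meant to supply an effect size?

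*Combined protocol and SAP*

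**What the plan says.** Section 4 fixes the design: "participants will be randomized in equal numbers and representation to receive one of four (4) theoretical-based graphic messages". The total is 360, half African American and half Latino, which is 90 per message overall and 45 per message within each group. Section 8 makes susceptibility immediately after exposure the primary outcome, measured by three items each coded 1 to 4.

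Section 17 defines a binary susceptibility outcome, analysed by logistic regression, and an aggregated score, analysed by ANCOVA. On reporting it says "Mean and median will be presented for continuous variables, and frequencies will be presented for categorical variables", and on testing "inflated type I error rate will be adjusted in multiple testing". The power paragraph gives the purpose, "The goal of this pilot analysis is to provide preliminary data for future studies, including the possible effect size", and then its only number: "we expect the effect size to be 1.05 (standardized mean difference in the aggregated score) between message groups". Section 18 identifies a funding call "to pursue support for this line of research through the trans-NIH Tobacco Regulatory Science Program".

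No section says where 1.05 came from, which SD it is scaled to, what significance level or power was used, how 360 was reached, or whether intervals will be reported.

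**The concern.** If the possible effect size is a named product of the pilot, its precision matters more than power against a guessed value. Yet the plan names summaries, models and adjusted tests, and no interval. The single planning figure is very large for a comparison of four active messages and cannot be checked. It is also unconnected to the sample size, since 360 is far more than 1.05 requires.

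Two harms could follow. First, if only the pairs that pass an adjusted test are carried forward, their estimates run high and a follow-on study sized on them is too small. Second, a non-significant pair might be read as two messages working equally well, when 90 per message leaves a fairly wide interval.

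**Working it through.** **Inputs from the documents.** Total 360, four equal arms, so n = 90 per message; expected standardized difference d = 1.05; ANCOVA for the score.

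**Assumptions, because the documents give none.** Two-sided 5%; 80% or 90% power; Bonferroni over six pairs as an illustrative adjustment; baseline score as the covariate; pre-post correlation r from 0.3 to 0.85; equal baseline and post-exposure SDs.

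**1. Can 360 be reproduced?** No, because level, power and SD are missing. What can be asked is whether 90 per message is enough for 1.05. The normal approximation per arm is n = 2(z₁₋α/₂ + z_power)²/d². At 5% and 80% this is 2(1.960 + 0.842)²/1.05² = 14.2. With the t distribution:

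| Level | 80% power | 90% power |
|---|---|---|
| 0.05 | 15.3 | 20.1 |
| 0.05/6 | 23.8 | 29.7 |

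Rounded up, that is 16 to 30 per arm, or 4 × 16 = 64 to 4 × 30 = 120 in total, without any gain from the covariate. Power at 90 per arm exceeds 0.9999 at both levels.

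**2. What precision does 90 per message give?** SE = √(1 − r²) × √(2/90), with √(2/90) = 0.149. The 95% half-width is t(355) × SE, where 355 = 360 − 4 − 1 and t is about 1.967. The detectable difference at 80% power is about 0.42√(1 − r²) for one pair and 0.52√(1 − r²) with six-pair Bonferroni.

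| r | SE | 95% half-width | Detectable, one pair | Detectable, six pairs |
|---|---|---|---|---|
| 0.3 | 0.142 | 0.28 | 0.40 | 0.50 |
| 0.5 | 0.129 | 0.25 | 0.36 | 0.45 |
| 0.7 | 0.106 | 0.21 | 0.30 | 0.37 |
| 0.85 | 0.079 | 0.15 | 0.22 | 0.28 |

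Units are raw SD. At r = 0.3 an observed difference of 0.20 would have the interval 0.20 ± 0.28, that is −0.08 to 0.48.

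**3. How large could selection bias be?** Suppose a true difference of 0.3 SD, and that only significant pairs are carried forward. With threshold c = t(355, 0.05/12) × SE and k = (c − 0.3)/SE, the mean significant estimate is close to 0.3 + SE × φ(k)/[1 − Φ(k)]. At r = 0.3, c = 0.377 and k = 0.54, giving about 0.47. A two-arm follow-on sized on that mean for 80% power has the following true power:

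| r | Mean, six-pair Bonferroni | True power | Mean, no adjustment | True power |
|---|---|---|---|---|
| 0.3 | 0.47 | 44% | 0.40 | 56% |
| 0.7 | 0.37 | 62% | 0.34 | 71% |
| 0.85 | 0.32 | 76% | 0.31 | 79% |

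If every estimate is reported, the mean is 0.3 and there is no such bias. The whole effect comes from the selection rule.

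**4. Does the plan contain that rule?** Section 17 says that multiple testing will be adjusted for. It does not say that non-significant estimates will be withheld. Section 18 names a funding call. It does not say that a later study will be sized on significant pairs, or that it will compare two of these messages with each other. Against a no-message control, these pairwise differences would not be the sizing input.

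**5. Is anything missing that the analysis needs?** The score, model, comparison and metric are all named. ANCOVA returns an adjusted difference and its SE; logistic regression returns a log odds ratio and its SE. The intervals follow directly from these.

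**The case for a change.** The strongest case for acting is that a sentence would be cheap and that estimation is what a pilot is for. A paragraph headed as a power analysis contains no power calculation, and the missing SD leaves the figure open to different readings. If 1.05 were raw score points, 90 per message would give 80% power at an SD of about 2.5; as a true standardized difference it needs at most 30. With four active messages, differences well below 1.05 are plausible, and for those the precision in step 2 is what counts. A plan that mentions only adjusted tests also does nothing to discourage reporting by significance.

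Much of this stands as comment on the documentation: 1.05 cannot be verified, 360 has no stated basis, and intervals are not mentioned. Three things limit it. The text does label 1.05 as standardized and tied to the aggregated score, so what is missing is the standardizer and the sum-or-mean rule. The effect size is one named part of the pilot's purpose, not all of it. And the 44% figure combines a 0.3 SD effect, low r, Bonferroni over six pairs, selective use of results and a two-arm follow-on.

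Writing expected half-widths into the plan would bring its own difficulty. They hold only if the post-exposure SD equals the baseline SD. If the ratio were 0.8 or 1.2, the 0.28 would become 0.28 × 0.8 = 0.22 or 0.28 × 1.2 = 0.34. Never-users answering items whose lowest category is a firm refusal may sit at the floor, so equality should not be presumed.

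**Conclusion.** No change follows. This is a gap that analysts fill sensibly: the rationale for 1.05 and for 360 is undocumented, but no stated figure is shown to be wrong, enrolment is ample for the stated effect, and the models already planned supply every between-message contrast with its uncertainty, for the score and for the binary outcome alike. Reporting those contrasts with 95% intervals whatever their significance is ordinary practice and is compatible with the plan as written.

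The adequacy of 90 per message for 1.05 holds across the levels and powers tried, provided that 1.05 is a standardized difference, as the text says. The precision figures depend on the assumed correlation and equal SDs. The follow-on power figures are illustrative and apply only under selection by significance, which the documents do not plan.

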18. FUTURE RESEARCH PLANS

We will report the results of this research in one or more publications in academic journal(s) to advance knowledge pertaining to effective communication with Latino and African American adolescents regarding vaping prevention. Additionally, we will disseminate our findings at national and international conferences. We have identified a request for applications

to pursue support for this line of research through the trans-NIH Tobacco Regulatory Science Program (RFA-OD-19-019). An FDA and NIH defined priority research area is to understand how to effectively communicate to the public and vulnerable populations regarding nicotine and the health effects of tobacco products.

20. APPENDIX

Financial reward

Health reward

Social norms

Self-efficacy

LAS COMPAÑÍAS DE
CIGARRILLOS ELECTRÓNICOS
SE ESTÁN ENFOCANDO
EN LOS ADOLESCENTES
AFROAMÉRICANOS Y
LATINOS.

TU VIDA ES
IMPORTANTE.
NO DEJES QUE
TE LA QUITEN.

CONFIDENTIAL
